14.2. Sample Size Justification

This study was designed and powered to show non-inferiority of the Test lens compared to the Control lens with respect to CLUE Comfort, logMAR Visual Acuity and Slit Lamp Findings (Grade 3 or higher). It was assumed there was no difference between the Test and Control lens with respect to CLUE comfort, visual performance and slit lamp findings.

In addition to the endpoints mentioned above this study was also powered to demonstrate the proportion of eyes with acceptable fitting on the Test lens is significantly superior to 90% as well as the cumulative odds ratio of (individual reduction items) the Test lens compared to the control lens is significantly superior to 1.00.

Unless otherwise specified, the sample size was calculated to achieve a minimum statistical power of 80% and a type I error of 5%.

The sample size calculation was based on historical data from a four similar randomized bilateral multi-site studies [REDACTED] where the same Test and Control lenses were used. Both lenses were worn as daily wear for at least 5 days per week for at least 6 hours per day. Follow-up visits occurred at 1 and 2-weeks after the initial visit. Subject accountability for each study is listed in Table 4 below.

[REDACTED]		
[REDACTED]	[REDACTED]	[REDACTED]

Table 6: Descriptive Summary of Slit Lamp Findings Pooled Across Historical Studies

%= nx100/N; SD=Standard Deviation

¹All SLF reported for this study are combined for the purposes of summarizing

² The percent (%) of Any Grade 2 is calculated using the Total Unique Eyes as the denominator

CLUE Comfort

Sample size calculation for CLUE comfort was carried out using an approximation of the power of an F-test derived from the non-centrality parameter calculated from the observed F statistic of a linear model⁸.

Model details:

CLUE comfort was analyzed using a linear mixed model. Lens type, period and the interaction between lens type and period were included in the model as fixed effects. A compound symmetric (CS) covariance was used to model the correlation between measurements on the same subject across study periods. Below is the variance-covariance matrix used in the CLUE Comfort model.

$$\sum_{comfort} \begin{pmatrix} 202 & 105 & 105 \\ 105 & 202 & 105 \\ 105 & 105 & 202 \end{pmatrix}$$

Visual Performance

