All outdoor glare items are assessed using the same ordinal scale (1=Excellent ... 5=Poor). Outdoor Glare reduction items will be analyzed separately using a Bayesian multinomial model for ordinal data adjusting for baseline. The regression model will include sequence of lens wear, lens type, period and first order carryover effect. Clinical site and subject nested within clinical site will be included as random effects. Other subject characteristics such as age, gender, race and iris category will be included when appropriate.

The Model:

Let $y_{ijklm} = (y_{ijklm1}, y_{ijklm2}, y_{ijklm3}, y_{ijklm4}, y_{ijklm5})$ denote the rating for the m^{th} subject, from the l^{th} site, assigned to the i^{th} study lens in the j^{th} period using the k^{th} sequence. Possible values of y_{ijklm} are 1 if the subject rating of outdoor glare items are X and 0 otherwise (X=1 for Excellent and X=5 for Poor, respectively). The likelihood is constructed as follows:

$$y_{ijklm} \sim \text{Multinomial}(P_{ijklm1}, P_{ijklm2}, P_{ijklm3}, P_{ijklm4}, P_{ijklm5})$$

$$P_{ijklm1} = \gamma_{ijklm1}$$

$$P_{ijklmX} = \gamma_{ijklmX} - \gamma_{ijklm(X-1)} \quad 2 \leq n \leq 4$$

$$P_{ijklm5} = 1 - \sum_{x=1..4} P_{ijklmX}$$

$$\text{Logit}(\gamma_{ijklm}) = \theta_n + \beta_1 \text{Lens}_{i[j,k]} + \beta_2 \text{Period}_{j_1} + \beta_3 \text{Period}_{j_2} + \beta_4 \text{Sequence}_k + \beta_5 \text{Carry}_{i[j,k]} + \gamma_l + \delta_{m(l)}$$

Where θ_n is the intercept for levels $n=1,2,3,4$, $P_{ijklm1} = \Pr(\gamma_{ijklm1} = 1)$ with respect to outdoor glare preference. We assume the random subject effects are independent identically distributed (i.i.d) as $\delta_{m(l)} \sim N(0, \sigma_{subject/site}^2)$ for subject m nested within clinical site l and the random clinical site effects are i.i.d as $\gamma_l \sim N(0, \sigma_{site}^2)$ for $i=1,2$ (lens), $j=1, 2, 3$ (Period) $k=1, 2$ (Sequence) $l=1, \dots, 5$ (Site) $m=1, \dots, n_l$ (subject/site).

In this model, the lens i will be determined by the period j and sequence k , therefore i is denoted as a function of j and k . We define $Lens_i=0$ for the Control lens and $Lens_i=1$ for the Test lens. The odds ratio for having higher rating can be written as $OR=e^{-\beta_1}$.

Independent vague $N(0, 1000)$ priors for the regression coefficients β_i $i=1,\dots,5$. For θ_n , we are considering the following priors

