$$\begin{aligned}\pi_0(01) &\sim N(0, 100) \\ \pi_0(02 | 01) &\sim N(0, 100)I(\theta > 01) \\ \pi_0(03 | 02) &\sim N(0, 100)I(\theta > 02) \\ \pi_0(04 | 03) &\sim N(0, 100)I(\theta > 03)\end{aligned}$$

For the variance of random effects independent vague normal priors will also be used; $\sigma_p^2 \sim \text{inverse-gamma}(0.001, 0.001)$ and $\sigma_s^2 \sim \text{inverse-gamma}(0.001, 0.001)$. The Metropolis sample algorithm as implemented in the SAS/Stat MCMC Procedure will be used to estimate the posterior distributions of the unknown parameters. Inferences will be made based on the posterior credible interval for the relevant parameters.

Hypothesis Testing

The null and alternative hypotheses for superiority are as follows:

$$H_0 \text{ } OR \leq 1$$

$$H_A \text{ } OR > 1$$

Where OR represent the odds ratio of having higher rating of the Test lens compared to the Control lens. Superiority will be declared if the lower bound of the 2-sided 95% credible confidence interval is above 1, i.e. $P(OR=e^{-\beta_1}>1|y)=0.975$.

Indoor Glare Reduction

Indoor Glare reduction consists of 4 individual questionnaire items:

Each item will be analyzed individually and tested in the exact same manner as the Outdoor Glare Reduction Items described above.

Driving Measures

Driving measure consists of two individual questionnaire items:

Each item will be analyzed individually in the exact same manner as the Outdoor Glare Reduction Items described above. However the hypothesis test will be as follows:

Hypothesis Testing

The null and alternative hypotheses for superiority are as follows:

$$H_0 \text{ } OR \leqslant 0.67$$

$$H_A \text{ } OR > 0.67$$

Where OR represent the odds ratio of having higher rating of the Test lens compared to the Control lens. Non-inferiority will be declared if the lower bound of the 2-sided 95% credible confidence interval is above 0.67, i.e. $P(OR = e^{-\beta_1} > 0.67 | y) = 0.975$. Superiority will be declared if the lower bound of the 2-sided 95% credible interval is above 1, i.e. $P(OR = e^{-\beta_1} > 1 | y) = 0.975$. Superiority will only be tested in the event that non-inferiority is established.

Other safety analysis:

Not Applicable

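### The odds ratio for the outdoor, indoor and driving items points the wrong way: as defined, a value above 1 means the Test lens is rated worse

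*Combined protocol and SAP*

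**What the plan says.** Section 14.7 (Other Exploratory Analyses, Outdoor Glare Reduction) sets out a cumulative-logit model.

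- **Scale.** "All outdoor glare items are assessed using the same ordinal scale (1=Excellent ... 5=Poor"). The likelihood repeats the coding: "X=1 for Excellent and X=5 for Poor, respectively".
- **Cumulation.** The first category probability equals γ1, and each later one is γX minus γ(X−1).
- **Lens effect.** The logit of γ is θn + β1·Lens plus other terms, with Control = 0 and Test = 1.
- **Odds ratio.** "The odds ratio for having higher rating can be written as $OR=e^{-\beta_1".
- **Outdoor rule.** "Superiority will be declared if the lower bound of the 2-sided 95% credible confidence interval is above 1".
- **Indoor items.** They use the same model and the same test as the outdoor items.
- **Driving items.** They use the same model, and exp(−β1) is written out again: "Non-inferiority will be declared if the lower bound of the 2-sided 95% credible confidence interval is above 0.67", with superiority tested at 1 afterwards.

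Section 2.3 gives the intent: Test superior on at least 2 of 4 outdoor and at least 2 of 4 indoor items, and non-inferior on both driving items. Section 14.2 adds that the study was also powered to show that the cumulative odds ratio for the individual reduction items of "the Test lens compared to the control lens is significantly superior to 1.00".

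**The concern.** On this scale a low code is good, and the model cumulates from the good end. A positive β1 therefore favours the Test lens, yet the plan changes the sign before forming the odds ratio and then treats large values as success. Followed literally, the rule would report a real improvement as a failed item and a real deterioration as superiority. For driving, the 0.67 margin would guard against the wrong thing. Up to ten items are affected: four outdoor, four indoor and two driving. (Section 2.2 counts three indoor items; Sections 2.3 and 14.7 count four.) According to the synopsis, the study is meant to inform later Design Validation or Claims studies, so a reversed result here could carry forward.

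**Working it through.** **1. The plan's own figure.** Section 2.3 (Justification of Clinical Margins) equates a cumulative odds ratio of 0.67 with a difference of at most 10% in cumulative proportion. The largest difference over all starting proportions is tanh(ln(1/0.67)/4) = tanh(0.4005/4) = 0.0998. The 10% is reproduced, so the margin is sound for a cumulative odds ratio. What remains is the direction in which it is applied.

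**2. Direction of γ.** From P1 = γ1 and PX = γX − γ(X−1), it follows that γX = P1 + … + PX = P(code ≤ X), the probability of category X or better. The priors agree, since each θ is constrained to exceed the one before it.

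**3. Direction of β1.** With logit P(code ≤ n) = θn + β1·Lens and the other terms held fixed,

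exp(β1) = odds(code ≤ n on Test) / odds(code ≤ n on Control).

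This is the odds ratio for a *better* rating. Its reciprocal, exp(−β1), is the odds ratio for a higher code, that is, a *poorer* rating.

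**4. What the rules then require.**

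- Superiority: exp(−β1) > 1 means β1 < 0, so Test is rated worse.
- Driving non-inferiority: exp(−β1) > 0.67 means exp(β1) < 1/0.67 = 1.49. This limits how much better Test may be and sets no limit on how much worse.

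**5. Numerical example.** Assume Control cumulative probabilities of 0.20, 0.50, 0.80 and 0.95. Multiply each cumulative odds by exp(β1) and convert back. For P(Excellent) at exp(β1) = 0.5: 0.25 × 0.5 = 0.125, and 0.125/1.125 = 0.111.

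| exp(β1) | Plan's OR, exp(−β1) | P(Excellent) | P(Poor) | Mean code | Test is |
|---|---|---|---|---|---|
| 2 | 0.5 | 0.333 | 0.026 | 2.14 | better |
| 1 | 1 | 0.200 | 0.050 | 2.55 | equal |
| 0.5 | 2 | 0.111 | 0.095 | 2.98 | worse |

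Two other assumed Control distributions (0.35/0.70/0.90/0.98 and 0.10/0.30/0.60/0.85) give the same direction.

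**6. How often the rule would mislead.** The simulation used the first Control distribution, 120 independent ratings per lens (120 being the target number of completers), 300 trials per row, a proportional-odds maximum-likelihood fit, and a Wald 95% interval in place of the credible interval.

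| True odds ratio for a better rating on Test | Superiority, as written | Superiority, sign corrected | Driving non-inferiority, as written | Driving non-inferiority, sign corrected |
|---|---|---|---|---|
| 2 (better) | 0% | 86% | 0% | 99.3% |
| 1 (equal) | 3% | 2% | 43.7% | 39.3% |
| 0.5 (worse) | 80% | 0% | 99.7% | 0% |

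The simulation ignores within-subject correlation, period and carryover. Its percentages illustrate direction and are not operating characteristics of this trial.

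**The case against.** The strongest reply concedes the outdoor algebra and contests its reach and weight.

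- **Scope.** The 1-to-5 scale is stated only for the outdoor items; the indoor and driving response options are not visible. If an unseen item were coded with higher as better, exp(−β1) would be right for it. This stands as a qualification. However, Section 14.7 applies the outdoor model to both sets without giving another scale, so the text as written carries the reversal to them.
- **Diagnosis.** *Higher rating* can mean a numerically higher code, and exp(−β1) is then correctly labelled. That is true, but a value above 1 still cannot mean superiority. If the phrase means a better rating, the formula is wrong. Both readings leave the rule at odds with Section 2.3.
- **Consequence.** These are exploratory hypotheses, and Section 2.3 makes study success depend on the primary and secondary ones. The frequency tables by lens would probably expose a reversed conclusion, and Section 14.10 allows documented changes. This limits the severity. It does not make the rule right, and a sign changed after the data are seen would look post hoc.
- **Power statement.** Section 14.2 concerns the reduction items against 1.00, not driving, and Table 7 gives no sample size or power for any of these items. That is correct, so the power statement adds little weight.
- **Simulation.** The effects and distributions are assumed. This is accepted; the conclusion rests on steps 2 to 4.

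**Conclusion.** The concern holds. For the four outdoor items, the coding, the model and the decision rule contradict one another by algebra, whatever the true distributions: the rule declares superiority for a lens that is rated worse. Through the cross-references the same applies to the indoor items and to the driving margin, provided those items use the same 1 = Excellent to 5 = Poor scale, which the sponsor should confirm. If the rule were followed literally, moderate effects would usually give the wrong answer: in the illustration, 80% false superiority for a halved odds of a better rating, and none for a doubled one. The primary and secondary analyses are not affected. This should be corrected before database lock.

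**What to change.** In Section 14.7, define the odds ratio as exp(β1), the odds of a better rating (lower code) on Test relative to Control. Make the change in all four places where exp(−β1) appears: the model description, the outdoor rule, and the driving non-inferiority and superiority rules. Replace *higher rating* by *better rating* in its three places, and add a sentence saying that values above 1 favour Test. The hypotheses and limits can stay as they are: above 1 for outdoor and indoor, above 0.67 and then above 1 for driving.

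Reverse-scoring the items so that 5 = Excellent while keeping exp(−β1), or entering the lens term as −β1·Lens while keeping exp(−β1), would do the same job. Only one of the three changes should be made, because two would cancel.

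State the response scale for the indoor and driving items. Carry the correction into the separate SAP that Section 14.3 says takes precedence, if the sign was copied there.

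The cost is a few edits to the text and the matching line of analysis code. No data, visits or sample size change.

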14.8. Interim Analysis

There will not be an interim analysis performed on this study.

14.9. Procedure for Handling Missing Data and Drop-Outs

Missing or spurious values will not be imputed. The count of missing values will be included in the summary tables and listings.

Subject dropout is expected to be one of the main reasons of missing data in this clinical trial. Past clinical trials don't provide the evidence that subject dropout is systematic or not-at-random. To evaluate the impact of missing data, sensitivity analysis will be conducted using multiple imputation methods if the proportion of subject dropout is greater than the 15%. The

SAS/STAT procedures PROC MI and PROC MIANALYZE will be utilized with a parametric regression method used to make at least 10 imputations.

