4.3. Enrollment Target and Study Duration

Approximately 130 subjects will be enrolled to ensure that at least 120 subjects will complete the study. Enrolled subjects will be habitual wearers of spherical contact lenses. All subjects will be the age of 18 and ≤ 49 years old. Eligible presbyopes will be those that wear full distance contact lenses in both eyes, then wear reading glasses over them. Subjects will wear the Test and Control contact lenses bilaterally approximately 2 weeks each on a daily wear (DW) basis, then wear either the Test or Control lens again for 2 weeks, for a total study duration of approximately 42 days (6 weeks) per subject.

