1.23	Subjective Lens Fit Assessment	
Subjective Assessment of the Lens Fit. If the fit is graded as unacceptable based on the criteria below, then the subject is discontinued from the study and will not be replaced.
 
 1. Limbal exposure in any gaze 2. Edge lift 3. Insufficient and/or excessive movement in all three movement categories
1.24	Continuance	
For the subject to continue in the study, they must meet all three of the following criteria:
 
 1. Snellen visual acuity is 20/30 or better OD and OS 2. The lens fit is acceptable OD and OS 3. Investigator approval. If the Investigator does not approve the dispensing of the first study lens, then the study is terminated for that subject.
1.25	Dispense	
The lenses will be dispensed for 6-8 days
 
 1. The subjects should wear their lenses similar to the inclusion criteria: ≥ 6 hours

Visit 1: Treatment 1 Lens Fitting		
Step	Procedure	Details
		
per day, ≥ 5 days per week.
 
 2. The lenses will be worn as daily wear only. 3. All subjects will be provided Opti-Free® PureMoist® to be used in a rub regime. 4. Preservative-free rewetting drops are permitted if needed. 5. A patient instruction booklet will be provided. 6. The lenses must be stored in the supplied case out of direct sunlight. 
Note 1: In the event a lens is lost or damaged, the subject will return to the investigator site for replacement (extra lenses cannot be given at the dispensing visit).
 
Note 2: The subject's habitual contact lenses cannot be worn at any time during the study.

VISIT 2

The follow-up will occur 6-8 days after the initial dispensing. The subjects must enter the visit wearing their study contact lenses.

Visit 2: Treatment 1 Follow-Up 1		
Step	Procedure	Details
2.1.	Adverse Events and Concomitant Medications Review	
Review the subject's concomitant medications and record any changes from the previous study visit.
 
Record any adverse events or medical history changes from the previous study visit.

2.2.	Wearing Time	Record the average wearing time and comfortable wearing time.
2.3.	Compliance	Confirm compliance with the prescribed wear schedule. Outdoor and total hours will be asked.
2.4.	Subject Reported Ocular Symptoms	Subjects will respond to a verbal open-ended symptoms questionnaire.

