8.2. Withdrawal/Discontinuation from the Study

A subject will be withdrawn from the study for any of the following reasons:

- Subject death during the study period
- Subject withdrawal of consent
- Subject not compliant to protocol (e.g. Subject more than 2 days out of visit window).
- Subject lost to follow-up
- Subject no longer meets eligibility criteria (e.g. the subject becomes pregnant)

- Subject develops significant or serious adverse events causing discontinuation of study lens wear (subjects missing more than 2 days of missed lens wear within a period 1 of week should be discontinued)
- Subjects who have experienced a Corneal infiltrative Event (CIE)
- Investigator's clinical judgment regarding the subject safety reasons (that it is in the best interest of the subject to stop treatment)
- Subject missed any scheduled study visits
- Subject not compliant with study lens wear schedule
- Subject not successfully dispensed due to lack of efficacy and safety including poor vision, poor comfort or unacceptable fit

For discontinued subjects, the Investigator will:

- Complete the current visit (scheduled or unscheduled)
- Complete the Final Evaluation, indicating the reason that the subject was discontinued from the study
- Record the spherocylindrical refraction with best corrected distance visual acuity
- Collect used test article(s) (worn or brought to the visit) from the subject and discard them, unless otherwise stated in Section 0
- Collect all unused test article(s) from the subject

Investigator will discuss with sponsor before enrolling any additional subjects if a subject discontinues from the study prematurely.

In cases where a subject is lost to follow-up, every possible effort must be made to contact the subject and determine the reason for discontinuation/withdrawal. The measures taken to follow up must be documented including two written attempts and a certified letter (or equivalent) as the final attempt.

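### The missing-data sensitivity analysis is conditional on more than 15% dropout, about twice the planned loss, although the protocol removes subjects by rule for poor lens outcomes

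*Combined protocol and SAP*

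**What the plan says.** Section 14.9 sets the main rule: "Missing or spurious values will not be imputed". A sensitivity analysis by multiple imputation follows only "if the proportion of subject dropout is greater than the 15" per cent, "with a parametric regression method used to make at least 10 imputations". The imputation variables are not named, and no missing-not-at-random scenario is given. The justification is: "Past clinical trials don't provide the evidence that subject dropout is systematic or not-at-random".

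Section 4.3 gives the planned loss indirectly: "Approximately 130 subjects will be enrolled to ensure that at least 120 subjects will complete the study".

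Other sections remove subjects because of how a lens performed:

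- **Fit.** At every fit assessment in Section 7.2 (steps 1.23, 2.8, 3.9, 3.22, 4.9, 4.22, 5.8), if the fit is unacceptable, "then the subject is discontinued from the study and will not be replaced".
- **Acuity.** Steps 1.24, 3.23 and 4.23 require Snellen acuity of 20/30 or better in each eye for the subject to continue after a lens fitting.
- **Slit lamp.** Steps 2.11, 3.12 and 4.12 end participation, after resolution, for findings above Grade 2. Section 8.2 also withdraws subjects with a corneal infiltrative event.
- **Dispensing.** Section 8.2 lists "Subject not successfully dispensed due to lack of efficacy and safety including poor vision, poor comfort or unacceptable fit".

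Section 8.1 places randomised subjects who do not complete dispensing in a category apart from those discontinued, and draws the safety and efficacy sets from dispensed subjects. Section 14.3 defines an ITT set of all randomised subjects with at least one observation.

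**The concern.** The condition rests on the history of other trials, while this protocol makes some loss depend on the lens outcome. In a non-inferiority comparison, losing poor experiences with one lens tends to move the result towards non-inferiority. For the fit endpoint, tested against 90%, removing failing eyes from later assessments raises the observed acceptance rate. Section 2.3 requires all primary and secondary hypotheses to be met, so each of these results counts.

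Up to 19 of 130 subjects could be lost with no sensitivity analysis required. If the analysis did run, regression imputation as described assumes missing at random. The CLUE and acuity models in Section 14.5 contain neither fit nor slit-lamp grade, so the recorded reason for removal does not enter them.

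**Working it through.** **1. Planned loss and trigger.** Inputs: 130 and 120 (Section 4.3), 15% (Section 14.9). Implied loss = 10/130 = 7.7%. 15% of 130 = 19.5, so the condition needs 20 losses (20/130 = 15.4%); 19 losses (14.6%) do not meet it. The binomial probability of 20 or more losses among 130 is:

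| True loss rate | P(20 or more) |
|---|---|
| 7.7% | 0.23% |
| 10% | 3.4% |
| 12% | 14.7% |
| 15% | 48.9% |

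**2. Could outcome-driven removal reach the trigger?** Section 14.2 assumes 95% acceptable fit, with correlation 0.80 within a period and 0.50 across periods. I added these assumptions: a Gaussian latent model, one assessment per period, the same rate on both lenses, and a further 7.7% lost for other reasons. Total loss = 1 − (1 − fit removals) × (1 − 0.077).

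| Fit rate per eye | Subjects failing in any of 3 periods | Total loss | P(20 or more) |
|---|---|---|---|
| 95% | 10.4% | 17.3% | 75% |
| 97% | 6.3% | 13.5% | 30% |
| 98% | 4.3% | 11.6% | 12% |
| 99% | 2.2% | 9.7% | 2.6% |

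Section 14.2 calls 95% conservative, so whether the condition is met depends heavily on a rate not yet known.

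**3. Which CLUE and logMAR values are lost?** At Visits 3, 4 and 5 both are recorded before the fit and slit-lamp checks (3.6 and 3.8 before 3.9 and 3.12; 4.6 and 4.8 before 4.9 and 4.12; 5.5 and 5.7 before 5.8 and 5.11).

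- Test/Control/Control, removed at Visit 3: the Test values are kept and both Control periods are lost.
- Control/Test/Test, removed at Visit 4: the first Test period is kept and the repeat is lost.
- Removed at Visit 5: nothing is lost.
- Failure at a lens fitting (1.23–1.24, 3.22–3.23, 4.22–4.23): the 2-week values for that lens in that period are never obtained. In Control/Test/Test, failing at 3.22–3.23 loses both Test periods.
- Removed at Visit 2: a one-week CLUE exists (step 2.6), but no 2-week CLUE or logMAR value.

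**4. Size for CLUE comfort.** The lens contrast is (1, −1, −1)/3 between sequences. With variance 202 and covariance 105 (Section 14.2), its variance per subject is (3 × 202 − 2 × 105)/9 = 44. As a check on Table 7, with 60 subjects (30 per sequence) the variance is 44 × 2/30 = 2.93. With margin 5 and 58 df this gives 81.9% power, against the 80% stated.

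At 120 completers: SE = √(44 × 2/60) = 1.21 and the 95% half-width is 2.37. If the lenses are equal, the expected lower limit is 5 − 2.37 = 2.63 points above the margin.

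Bias = fraction lost × assumed deficit, with every loss on Test. The 10 to 20 point deficit (0.5 to 1 CLUE population SD) is an assumption.

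- 7.7% lost: 0.077 × 10 = 0.8; 0.077 × 20 = 1.5 points.
- 14.6% lost: 0.146 × 10 = 1.5; 0.146 × 20 = 2.9 points.

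At 7.7% lost, using up the 2.63 points would take a deficit of 2.63/0.077 ≈ 34 points. Moving the mean by the full margin would take 5/0.077 = 65 points, or 0.05/0.077 = 0.65 logMAR.

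**5. Size for fit and slit-lamp findings.** In the model of step 2 at 95%, removal after the first failing period raises expected observed acceptance from 95.0% to 97.1%. As an extreme bound, count every missing Test eye as a failure, with the missing share equal to the dropout share:

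- Fit: 95% × (1 − 0.077) = 87.7%; at 14.6% missing, 81.1%. The estimate falls below 90% once 1 − 0.90/0.95 = 5.3% is missing, which is 7 of 130 subjects.
- Slit lamp, with the plan's 0.5% incidence on both lenses: the difference becomes 0.995 × m for missing share m, which is 7.7 points at 7.7% missing, against a 5-point margin.

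**The case against.** Several points on the other side stand. The visit order in step 3 means that most removals at 2-week visits keep the poor CLUE and acuity values. A reader might infer that the protocol discards the worst Test experiences in general; it does not. A reader might also take Section 8.2 to withdraw anyone with poor comfort or vision during wear. That clause concerns unsuccessful dispensing, and the 20/30 rule likewise applies at lens fittings only.

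It is also tempting to say that the condition will never be met. The documents do not support that: 7.7% is derived from approximate figures, and step 2 shows routes past 15%.

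The CLUE figures are one-sided. The same removal rules apply to both lenses, which share material, base curve and diameter (Table 1), and the deficit has no source in the documents. At planned loss, the worst illustrated case leaves the lower limit near −3.9 (−2.37 − 1.5), still inside −5.

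Removal that depends on recorded values can be missing at random if those values are in the model. That is correct in principle, but the Section 14.5 models for CLUE and acuity omit fit and slit-lamp grade, and Section 14.9 names no imputation variables. Section 8.2 has the failing visit completed, and Section 14.3 defines an ITT set; neither supplies later outcomes.

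Section 14.3 also announces a separate SAP that would override this text. None was available to check.

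**Conclusion.** The concern holds in this limited form and is worth acting on. The condition makes a sensitivity analysis very unlikely at the planned loss (about 0.2%), and its justification does not describe a protocol with outcome-based removal. If the condition is met, the planned imputation still assumes missing at random.

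For CLUE and logMAR the exposure is mainly failures at lens fittings and Visit 2 removals. The likely CLUE bias at planned loss is small, at most about 0.8 to 1.5 points under the stated assumptions. A reader might infer that the comfort or acuity conclusion is unsafe; the figures do not show that.

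Fit acceptance and slit-lamp findings are more exposed, because the event itself ends follow-up. The bounds in step 5 are extremes, not forecasts. They show that the planned number of losses is enough to matter for these two endpoints under the harshest reading.

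A related gap is that subject dropout is not defined for the 15% rule: neither the denominator nor the treatment of dispensing failures is given. Sections 8.1 and 14.3 also differ on whether randomised subjects who fail dispensing can be analysed.

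**What to change.** - Delete the 15% condition in Section 14.9 and always run the sensitivity analysis, on all randomised subjects including those who fail dispensing. Reconcile Section 8.1 with the ITT definition in Section 14.3 accordingly.
- For subjects removed for fit, vision, comfort or slit-lamp reasons, impute the missing CLUE and logMAR values for the lens concerned with a shift against that lens, and increase the shift until the conclusion changes. Report that tipping point.
- Name the imputation variables. Fit, slit-lamp grade, the one-week CLUE score and the logMAR value taken at fitting are already collected.
- In a parallel analysis, count missing later Test-lens fit assessments and slit-lamp outcomes as unfavourable.

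The clinical removal rules stay unchanged. The synopsis allows replacement of discontinued subjects while the fit steps do not, and these passages should be reconciled.

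The cost is minor programming and one table. The drawback for the sponsor is that a less favourable sensitivity figure may be shown.
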